Dose Modification of copanlisib is described in Section 6.6.

Duration of Treatment:

Patients will be treated until one of the following events: disease progression, unacceptable adverse event(s), withdrawal of consent, general or specific changes in the patient's condition that render the patient unacceptable for further treatment in the judgment of the investigator.

Sample Size and Statistical Consideration:

The study will enroll 42 patients. The two arms will enroll patients in parallel and independently. Safety analysis will be done by pooling patients from the two arms together. Efficacy analysis will be conducted independently within each of the two arms (lymphoma, solid tumor).

Patients who do not complete the planned cycle 2 cycles of treatment, which is required for the first evaluation of response, will be replaced.

(a) The lymphoma arm will enroll 23 patients with FL.

- Simon's two-stage design (Simon, 1989) will be used. The null hypothesis that the true ORR rate is 41% will be tested against a one-sided alternative. In the first stage, 13 patients will be accrued. If there are 5 or fewer ORRs (**To be assessed after completing 4 cycles of the treatment**) in these 13 patients, the study will be stopped for futility. Otherwise, 10 additional patients will be accrued for a total of 23. The null hypothesis will be rejected if 14 or more ORRs are observed in 23 patients. This design yields a type I error rate of 5% and power of 80% when the true ORR rate is 67%. Assuming that the CR rate is 0.09 (2 out 23), with 23 subjects we will have 80% power to claim that the true CR is at least 30%.
- The reference range of ORR in FL is 40% (n = 16. Dreyling et al, Ann Oncol. 2017) to

59% (n = 104. Dreyling et al, J Clin Oncol. 2017).

• The reference CR rate is 14% (n = 104. Dreyling et al, J Clin Oncol. 2017).

(b) The solid tumor arm will enroll 19 patients with EC.

Simon's two-stage design (Simon, 1989) will be used. The null hypothesis that the true ORR rate is 0.10 will be tested against a one-sided alternative. In the first stage, 11 patients will be accrued. If there are 1 or fewer ORRs (To be assessed after completing 4 cycles of treatment) in these 11 patients, the study will be stopped for futility. Otherwise, if >=2/11 responses are observed, then 8 additional patients will be accrued for a total of 19. The null hypothesis will be rejected if 4 or more ORRs are observed in

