(RECIST) guideline. CT or PET/CT scan will be performed after every two 28-day cycles of. After cycle 4, if the patient has achieved CR, scans will be done every 3 cycles.

Data analysis:

All patients receiving at least one dose of copanlisib will be evaluable for toxicity and all patients completing at least one 28-day cycle of therapy (copanlisib plus ketogenic diet) will be evaluable for response and time-to-endpoint analyses.

Response will be estimated with exact 95% confidence intervals (CIs). We will estimate overall survival, progression-free survival, and duration of response using the Kaplan-Meier method. Group comparisons, between groups associated with different biomarkers described below, will be made using a two-sided log-rank test, and the estimated hazard ratios and 95% CIs will be calculated using Cox regression. Overall survival will be assessed post hoc in the trial patients. In the exploratory correlative biomarker analyses, any patients with assessable biological samples (blood, tumor etc) will be included. An association between disease outcome (complete response, partial response, stable disease, progression of disease, duration of response, and progression-free survival) and changes from baseline in biomarker concentrations as a function of treatment over time will be assessed. Because of sample size considerations, we will base group comparisons for these analyses on two-sample t test. We will do correlative studies including all enrolled patients that have adequate biological samples available for analysis. We plan to assess changes over time and estimate odds ratios using mixed-effects logistic regression models or a linear model if the sample sizes for comparison are too small. We will summarize continuous variables as means and SDs, and categorical variables as counts with percentages. We will not do multiple testing adjustments. All the analyses will be done with SAS version 9.4.

Study Rationale

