As we recently reported ketogenic diet can suppress hyperinsulinemia associated with PI3K inhibitors, leading to potentiation of the anti-tumor effects of PI3K inhibitors[79]. Copanlisib potently inhibits PI3K α and PI3K δ . It has been approved for the treatment of relapsed follicular lymphoma, based on ORR of 59% (84 of 142 patients)[83]. The CR rate in FL was 14%, and the median progression-free survival was 11.2 months. Copanlisib demonstrated encouraging clinical activity in marginal zone lymphoma (ORR 70% including 9% CR). While these results are clinically meaningful, FL and MZL inevitably develop resistance to copanlisib with time, even in those patients who initially respond to the therapy. Novel strategies to improve the efficacy of copanlisib in FL and MZL, by improving CR and PFS, may transform how we manage these incurable malignancies.

Interestingly, copanlisib has also demonstrated clinical activity in aggressive lymphomas in a smaller study of heavily pre-treated patients[84]. Objective responses were achieved in patients with DLBCL (one PR; ORR 6.7%), PTCL (two CRs, one PR; ORR 21.4%), MCL (two uCRs, five PRs; ORR 63.6%), and transformed FL (both PRs; ORR 33.3%). These results suggest that copanlisib warrants further investigation in aggressive lymphomas such as PTCL and DLBCL. In a Phase I study of both solid tumors and lymphoma, sixteen of 20 patients treated at the MTD had reduced ⁽¹⁸⁾FDG-PET uptake; 7 (33%) had a reduction >25%. One patient achieved a complete response (CR; endometrial carcinoma exhibiting both PIK3CA and PTEN mutations and complete PTEN loss) and two had a partial response (PR; both metastatic breast cancer). Among the nine NHL patients, all six with follicular lymphoma (FL) responded (one CR and five PRs) and one patient with diffuse large B-cell lymphoma had a PR by investigator assessment; two patients with FL who achieved CR (per post hoc independent radiologic review) were on treatment >3 years.

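### The FL complete-response power statement starts from an unexplained 9% although the protocol's own FL reference is 14%, and it treats the 30% alternative as a rate the trial could claim

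*Combined protocol and SAP*

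**What the plan says.** The statement closes the first bullet on the lymphoma arm in the Protocol Synopsis, under Sample Size and Statistical Consideration, after the Simon design for objective response rate (ORR). It reads "Assuming that the CR rate is 0.09 (2 out 23"), and continues "with 23 subjects we will have 80% power to claim that the true CR is at least 30" per cent. It gives no test, cutoff, alpha or sidedness for CR. The only error rate nearby belongs to the ORR design: "This design yields a type I error rate of 5% and power of 80% when the true ORR rate is 67" per cent, against a one-sided alternative.

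Two bullets later the same list says "The reference CR rate is 14% (n = 104"). The Study Rationale agrees: "The CR rate in FL was 14" per cent.

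CR in FL is a secondary objective, and the Study Rationale names better CR as one aim of the combination. The Data analysis section plans estimation: "Response will be estimated with exact 95% confidence intervals (CIs"). It sets no threshold for CR.

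**The concern.** There are two separate points.

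1. **The starting rate.** Power of about 80% at n = 23 makes sense only if 9% acts as a null and 30% as the alternative, although the text does not use those words. The protocol's own benchmark for copanlisib in FL is 14%. Power against 9% therefore does not answer whether the diet raises CR above that reference. The only other 9% CR rate in the documents is for "marginal zone lymphoma (ORR 70% including 9% CR"), a disease this trial does not enrol. Nothing links it to this calculation, so its role cannot be inferred.

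2. **The wording.** The 30% is the true rate at which power is evaluated. A significant result would support a CR rate above the null. It would not support a rate of at least 30%.

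A reader would take from the sentence that 23 patients are enough to show a useful gain in CR. An investigator could later cite it for a claim that the planned interval would not bear out.

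**Working it through.** **Inputs.** n = 23, CR rate 0.09 (2/23 = 0.0870), target 0.30, stated power 80%, and reference 0.14, all from the lymphoma-arm list. The planned interval is the exact 95% CI from Data analysis. No alpha is given for CR, so I show one-sided 5% (as for ORR), two-sided 5% and one-sided 10%. All 23 patients are assumed enrolled.

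**Formula.** For a rule that rejects at r or more CRs, the error is P(X ≥ r | n = 23, p0) and the power is P(X ≥ r | n = 23, 0.30), with X binomial.

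**Step 1: the plan's own figure, about 9% versus 30%.**
- Null 2/23: P(X ≥ 5) = 0.0445, so the one-sided 5% bar is 5. Power is 86.4%.
- Null exactly 0.09: P(X ≥ 5) = 0.0504, just over 5%, so the bar is 6 (error 0.014). Power is 73.1%.
- Normal approximation, power = Φ{[√n(0.30 − p0) − z√(p0(1 − p0))]/√(0.30 × 0.70)}: 83.5% to 84.7% two-sided 5%, 87.9% to 88.8% one-sided 5%. With continuity correction: 77.2% to 78.7% two-sided, 82.7% to 83.9% one-sided.

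These values straddle 80%. The figure is plausible for 9%, but it cannot be confirmed without the missing test details.

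**Step 2: the 14% reference as null, exact.**

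| Alpha | Bar | Error at 14% | Power at 30% | Missed |
|---|---|---|---|---|
| one-sided 10% | 6 or more | 9.2% | 73.1% | 27% |
| one-sided 5% | 7 or more | 3.3% | 56.0% | 44% |
| two-sided 5% | 8 or more | 1.0% | 38.2% | 62% |

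At 5%, the normal approximations for 14% versus 30% run from 49% to 67%. With the bar of 7, power reaches 80% only at a true rate of about 37%. The bar of 5 that serves for a null of 2/23 would be met 21.2% of the time if the true rate were 14%.

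**Step 3: what the planned interval would support.**

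| CRs of 23 | Exact 95% CI or lower limit |
|---|---|
| 5 (21.7%) | 7.5% to 43.7% |
| 7 (30.4%) | 13.2% to 52.9% |
| 8 (34.8%) | 16.4% to 57.3% |
| 11 (47.8%) | lower limit 26.8% |
| 12 (52.2%) | lower limit 30.6% |

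The lower limit clears 14% from 8 CRs, which has probability 38% at a true 30%. It clears 30% from 12 CRs, and P(X ≥ 12 | 0.30) = 0.021. For 12 or more CRs to have 80% probability, the true rate must be about 59%.

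**Step 4: the stage 1 futility stop.** With a true ORR of 67% and a true CR rate of 30%, allowing for the stop lowers power for 5 or more CRs from 86.4% to 84.4%, and for 7 or more from 56.0% to 55.3%. Ignoring it slightly favours the plan.

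**For scale only.** Exact 80% power for 14% versus 30% at one-sided 5% first occurs at n = 40 (10 or more CRs, error 4.5%, power 80.4%).

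**The case against.** The strongest reply is that nothing in the plan depends on this sentence. CR is secondary, the planned analysis is an interval, and the sample size, futility stop and rejection rule all come from ORR. No rule compares the CR interval with 14%, so the 44% and 62% are consequences of tests the protocol never adopted. At one-sided 10%, the error level stated for the endometrial arm, the miss rate is 27%. Part of the loss at 5% is also discreteness, since the bar of 7 spends only 3.3%.

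Nor do 9% and 14% strictly contradict each other. One is an assumption and the other a published estimate. If 14% means 15 of 104 (my assumption), its exact 95% CI is 8.3% to 22.7%, which contains 9%. The ORR null of 41% also sits near the bottom of its stated 40% to 59% reference range, so a deliberately low null would fit the section. Finally, the text is a synopsis that points to sections not available here, and a reason for 9% may stand in one of them.

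Much of this stands, and it limits the weight of the point: the miss rates are conditional illustrations, and 9% may have been chosen on purpose. It does not rescue the sentence. Under each of the three alphas, exact power against 14% is below 80%, and so are the normal approximations at 5%. The claim of at least 30% is wrong whichever null is chosen, including a well-justified 9%.

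**Conclusion.** The concern holds on both points and should be fixed. The stated 80% is roughly right for 9% versus 30%, but 9% is unexplained beside the protocol's own FL figure of 14%. Against 14%, exact power at a true 30% is 56% at one-sided 5%, with a range of 38% to 73% over the alphas tried. This rests on treating 9% as the null, on an alpha that the documents do not supply for CR, and on all 23 patients being enrolled.

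The wording fault needs none of these assumptions: power at an alternative is not power to claim that alternative. On the planned 95% interval, a lower limit of at least 30% would be seen 2.1% of the time at a true rate of 30%. The primary ORR design is unaffected.

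**What to change.** Replace the sentence with text such as:

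> CR rate is secondary and will be estimated with an exact 95% CI. For orientation only, with 23 patients and a one-sided 5% exact test against the FL reference CR rate of 14% (7 or more CRs, error 3.3%), power is 56% if the true CR rate is 30% and 80% if it is about 37%.

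Alternatively, keep 9%, justify it against the 14% reference, and state the test, alpha, sidedness and cutoff. In that case describe the power as that of rejecting the 9% null when the true rate is 30%. Under either option, delete the phrase about claiming a true CR rate of at least 30%.

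The cost is one sentence. Sample size, stopping rules and the primary test stay as they are. With the replacement text, the stated power for CR becomes less favourable.

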PILOT PHASE II MULTICENTER STUDY OF THE PI3K INHIBITOR COPANLISIB IN COMBINATION WITH A KETOGENIC DIET IN THE TREATMENT OF PATIENTS WITH RELAPSED OR REFRACTORY FOLLICULAR LYMPHOMA OR ENDOMETRIAL CANCER

NCT04750941

Protocol date: 9/23/2024

PROTOCOL SYNOPSIS

Study Design: This is a multi-institution, open label, pilot phase II study of the PI3K inhibitor copanlisib in combination with a ketogenic diet in the treatment of patients with one of the following malignancies: (a) relapsed or refractory (R/R) follicular lymphoma (FL), (b) R/R endometrial cancer (EC) with a documented activating mutation in PIK3CA or loss of PTEN. The FL arm will enroll 23 subjects and the EC arm will enroll 19 subjects. The study will be stopped if the safety trigger is activated at the pre-specified times of interim safety analysis upon enrollment of 12 and 24 patients.

The two arms will enroll patients in parallel and independently. Safety analysis will be done by pooling patients from the two arms together. Efficacy analysis will be conducted independently within each arm.

Objectives: Primary Objectives

- Determine the objective response rate (ORR) (complete response [CR] + partial response [PR]) in FL.
- Determine the ORR in EC.

Secondary Objectives:

- Determine the CR and PR rates in FL upon completion of the study protocol.
- Determine the CR and PR rates in EC upon completion of the study protocol.
- Determine the ORR in FL and EC at the Simon stage I analysis
- Determine patient compliance with the ketogenic diet.

Exploratory Objectives:

- Determine the PD markers including *blood* levels of insulin, c-Peptide, BHB (beta-hydroxybutyrate), triglyceride, and glucose, and urine ketones.
- Determine the PD markers including levels of pINSR, INSR, pAKT, AKT, pS6, S6, Ki-67, TUNEL, caspase, and actin in paired pre- and post-treatment *tumor* tissues in patients who consented for the optional post-treatment biopsy of the tumors (blood and bone marrow are acceptable if they are known to be involved by lymphoma).
- Explore the correlation of disease response and the PD markers described above.
- Explore the correlation of disease response and gene alternations in tumor tissues.
- Explore the correlation of insulin response and gene alternations in normal buccal fibroblasts.
- Determine the change in body weight and body mass index (BMI) over time.
- Determine the change in computed tomography-based body composition metrics including

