The Phase II study will enroll 42 patients in two study groups. The lymphoma study group will enroll 23 patients with FL, and the solid tumor group will enroll 19 patients with EC.

In cycle 1, patients will first start ketogenic diet for 7 days (Day -6 to Day 0). Only patients who demonstrate compliance and tolerance with the ketogenic diet for all 7 days during the run-in

phase, as confirmed by pertinent blood and urine tests, will be allowed to continue the study and treatment using copanlisib and the ketogenic diet starting on day 1. In cycle 2 and beyond, patients will start the ketogenic diet and copanlisib on day 1.

Treatment Plan:

- Copanlisib: Copanlisib will be infused intravenously on days d1, 8, 15 of each cycle, over 1 hour, of 28-day cycles.
- Ketogenic diet:
 - Prior to the first treatment patients will start the ketogenic diet for 6 days (Day -5 to Day 0). Patients who demonstrate compliance and tolerance with the ketogenic diet, as confirmed by pertinent blood and urine tests and recorded dietary intake, will be allowed to continue the study and start copanlisib on Day 1. The ketogenic diet will continue daily throughout the treatment days.
 - In cycle 2 and beyond, patients will start the ketogenic diet and copanlisib on day 1. The ketogenic diet will then continue daily throughout the treatment days.
 - All patients will be eligible to receive the ketogenic diet as long as the patients remain on the trial. If patients want to remain on the trial to receive Copanlisib but wish to discontinue the ketogenic diet, they should do so at the following time: (a) when they have achieved a complete response, or (b) when they have completed 4 cycles of treatment. In the rare case when a patient wants to discontinue the ketogenic diet after having completed only 2 or 3 cycles of therapy but having not achieved a CR, the patient will be allowed to remain in the study and receive copanlisib without having to take the ketogenic diet. However, if a patient wishes to stop the ketogenic diet before

cycle 2 is completed, when the response will be first evaluated, the patient will not be allowed to continue this trial but will be replaced.

REGIMEN DESCRIPTION					
Agent	Premedications/Precautions	Dose	Route	Cycle Length	
Copanlisib	IV Hydration (Normal Saline 500 cc IV in 30 minutes after copanlisib infusion)	60 mg	IV over 60 minutes	28 days	
Ketogenic diet		Three times daily	Oral, three times daily		

Dose Modification:

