19 patients. This design yields a type I error rate of 10% and power of 81% when the true ORR rate is 30%.

Safety:

Patients will be monitored carefully for the development of adverse events (AEs). AE will be evaluated according to criteria outlined in the National Cancer Institute (NCI) Common Terminology Criteria for Adverse Events (CTCAE), version 5.

Safety Trigger

There will be ongoing safety monitoring.

Interim safety analysis will be performed upon enrollment of 12 and 24 subjects. Safety analysis will be done by pooling patients from the two arms together.

The safety trigger will be activated if any of the following Safety Trigger Events (STE) happens during the first cycle of treatment:

- During the interim analysis of the first 12 subjects: 3 incidents of STE excluding mortality, or 2 incidents of mortality deemed not likely to be due to progression of the cancer but possibly related to the treatment. The study will be stopped.
- During the interim analysis of the first 24 subjects: 5 incidents of STE excluding mortality, or 3 incidents of mortality deemed not likely to be due to progression of the cancer but possibly related to the treatment. The study will be stopped.

Safety Trigger Events (STE) will defined as the following:

- Any non-hematologic toxicity grade 3-4 that require delay of treatment by more than 7 days despite optimal management.
 - Note that a patient who experiences a STE may be allowed to continue the study, as long as the patient can safely resume therapy within 21 days.
- Any hematologic toxicity grade 3-4 that require delay of treatment by more than 7 days despite optimal management including blood products and growth factors.
 - Note that a patient who experiences a STE may be allowed to continue the study, as long as the patient can safely resume therapy within 21 days.

• Any mortality.

Efficacy Outcome:

Patients will be monitored for clinical and/or radiographic evidence of disease response. Response will be evaluated using clinical parameters, CT or PET/CT scan (PET/CT scan is preferred), and bone marrow or other tissue biopsy (when applicable for lymphoma), according to the Updated Recommendations for Evaluation, Staging, and Response Assessment for Hodgkin and Non-Hodgkin Lymphoma: The Lugano Classification. For solid tumor the response will be determined in accordance with the revised Response Evaluation Criteria in Solid Tumors

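### The safety looks are triggered by enrollment of patients 12 and 24, but the limits count first-cycle events that the newest patients cannot yet have shown

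*Combined protocol and SAP*

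**What the plan says.** The Study Design paragraph of the synopsis places the "interim safety analysis upon enrollment of 12 and 24 patients" and describes these times as pre-specified. The Safety Trigger section repeats it: "Interim safety analysis will be performed upon enrollment of 12 and 24 subjects". Patients from both arms are pooled.

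The trigger activates "if any of the following Safety Trigger Events (STE) happens during the" first cycle of treatment. The limits are:

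- Look 1: "During the interim analysis of the first 12 subjects: 3 incidents of STE excluding mortality", or 2 qualifying deaths.
- Look 2: "During the interim analysis of the first 24 subjects: 5 incidents of STE excluding mortality", or 3 qualifying deaths.

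A non-fatal STE is defined by its consequence: "Any non-hematologic toxicity grade 3-4 that require delay of treatment by more than 7 days despite optimal management". The hematologic definition has the same delay. The section also states "There will be ongoing safety monitoring", with no count or threshold attached.

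Under Treatment Plan, copanlisib is given on days 1, 8 and 15 of a 28-day cycle, after a diet run-in. The Study flow chart text gives that run-in as 7 days within cycle 1. The Treatment Plan gives it as 6 days, before the first treatment. Under Data analysis, patients are evaluable for toxicity once they have had at least one copanlisib dose.

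**The concern.** The look is tied to a date of entry, while the limits are tied to an outcome that takes weeks to appear. On the day patient 12 or 24 enrolls, that patient has had no copanlisib if enrollment precedes the run-in, and has only just had a first dose if enrollment is counted at day 1. Either way a delay of more than 7 days cannot yet have occurred. How many others are still incomplete depends on accrual, which the synopsis does not give.

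Limits of 3 in 12 and 5 in 24 make sense only if 12 and 24 patients have been observed. Set against fewer, they under-count. Late first-cycle events among the first 12 can still count at look 2. Late events among the last patients before look 2 fall at no later named look, although 42 patients are planned.

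The counted set is also open. The trigger counts subjects, whereas the toxicity-evaluable set requires a dose, so a patient who fails the run-in could fill one of the 12 places without exposure. The two run-in descriptions also leave it unclear whether a run-in event is a first-cycle event.

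**Working it through.** The synopsis states no target STE rate or stopping probability for this rule, so there is no figure of its own to reproduce.

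**1. Time needed to observe a patient**

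- Run-in plus cycle 1: 6 + 28 = 34 days, or 7 + 28 = 35 days.
- A toxicity that delays day 1 of cycle 2 is known only after a delay of more than 7 days, so add 8 days: 42 to 43 days.
- If enrollment is counted at first dose: 28 days, or 28 + 8 = 36 days.

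**2. Patients incomplete at a look**

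Assume evenly spaced accrual, with a gap of 30.44 / (patients per month) days. Count the newest patient and everyone enrolled less than one window earlier.

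| Window | 1/month | 2/month | 3/month |
|---|---|---|---|
| 28 days | 1 | 2 | 3 |
| 34–35 days | 2 | 3 | 4 |
| 36 days | 2 | 3 | 4 |
| 42–43 days | 2 | 3 | 5 |

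Only the newest patient is incomplete below 30.44/35 = 0.87 per month, or 30.44/43 = 0.71 per month with the longer window.

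**3. Effect on the chance of stopping**

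Assume independent patients, at most one STE each, a true STE rate p, and k patients at each look who contribute no events. Deaths are left out.

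- Look 1: P(X ≥ 3), X binomial on 12 − k patients.
- By look 2: 1 − Σ (x = 0 to 2) P(X = x) · P(Y ≤ 4 − x), Y binomial on the 12 patients newly observed between the looks.

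Worked case, p = 0.30 and k = 3, so 9 observed at look 1:

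- P(X = 0, 1, 2) = 0.0404, 0.1556, 0.2668, which sum to 0.4628. Look 1 stops with probability 1 − 0.4628 = 0.537.
- P(Y ≤ 4, 3, 2) = 0.7237, 0.4925, 0.2528. The sum of products is 0.0292 + 0.0767 + 0.0675 = 0.1733. Stopping by look 2 has probability 1 − 0.1733 = 0.827.

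Chance of stopping at look 1 / by look 2:

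| STE rate | k = 0 | k = 1 | k = 3 | k = 5 |
|---|---|---|---|---|
| 30% | 0.747 / 0.913 | 0.687 / 0.889 | 0.537 / 0.827 | 0.353 / 0.738 |
| 20% | 0.442 / 0.614 | 0.383 / 0.568 | 0.262 / 0.467 | 0.148 / 0.360 |
| 10% | 0.111 / 0.147 | 0.090 / 0.124 | 0.053 / 0.084 | 0.026 / 0.051 |

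The loss by look 2 for k = 1, 3, 5 is 2, 9 and 17 points at a 30% rate, and 5, 15 and 25 points at 20%.

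The death limit weakens in the same way. At an assumed 5% death rate, 2 or more of 12 has probability 0.118 with all observed, 0.102 with 1 unobserved and 0.071 with 3.

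**4. Allowing for partial observation**

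The table treats incomplete patients as contributing nothing. A delay of more than 7 days to the day-8 infusion is known by about day 16, to the day-15 infusion by about day 23, and to day 1 of cycle 2 by about day 37. Simulating STEs classified with equal chance at those three times (an assumption), with a 7-day run-in and even accrual, the loss by look 2 at 1, 2 and 3 patients per month is about 3, 6 and 11 points at a 30% rate, and about 6, 11 and 18 points at 20%.

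**The case against.** The strongest reply is that enrollment only names the cohort and the first-cycle window names the data, so the analysis of the first 12 subjects would naturally wait for their first cycle. On that reading the gap is an unstated data cut-off. The reading is possible, but nothing in the public text says that the look waits, and two places give enrollment as the time. The Simon futility looks do say when response is read: after 4 cycles. The safety look has no such clause.

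Second, the public text is a synopsis that refers to sections it does not include. One of those could state the data cut, and if so the timing point falls. This stands as a limit on the claim.

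Third, the binomial table overstates the loss, because patients part-way through cycle 1 can already have a classified event. That is right. The simulation shrinks the effect but does not remove it.

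Fourth, ongoing monitoring may catch late events. It may, but no stopping count is attached to it, and the limits are written to apply at the two looks.

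Finally, the toxicity-evaluable definition offers a natural way to exclude run-in failures. It does, but the trigger does not refer to it. The 6- versus 7-day conflict moves the window by one day and does not affect the conclusion.

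**Conclusion.** The concern holds for the synopsis as written. Followed literally, the rule compares 3 in 12 and 5 in 24 with counts from incompletely observed patients, and is less likely to stop the study than those limits suggest.

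The size depends on accrual and on the true STE rate, neither of which is documented. With one patient unobserved, as under slow accrual, the loss by look 2 is small: 91% to 89% at a 30% rate. At 2 to 3 patients per month, allowing for partial observation, it is about 6 to 11 points at a 30% rate and 11 to 18 points at 20%. With unobserved patients contributing nothing, 5 unobserved gives 17 and 25 points. This should be fixed, because the rule governs stopping the whole study and the correction is cheap. Confidence is medium, given the sections not in the public text.

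**What to change.** State that each look takes place when the first 12 (24) patients have completed first-cycle observation, including the time needed to classify a delay of more than 7 days, or have had an STE or left cycle 1 early. State whether enrollment continues meanwhile. Say whether the 12 and 24 are enrolled subjects or patients in the toxicity-evaluable set, and reconcile the two run-in descriptions, so that run-in failures do not dilute the count and it is clear how run-in events are handled.

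The costs are modest. Each look comes 34 to 43 days later. Without a pause in accrual, waiting days × monthly rate / 30.44 gives 1.1–1.4 further patients before each look at 1 per month, 2.2–2.8 at 2 per month and 3.4–4.2 at 3 per month. Stopping when toxicity is low also becomes more likely: by look 2 at a 10% STE rate it rises from 12%, 8% or 5% (1, 3 or 5 unobserved) to 15%, and at a 5% rate from 1.8%, 1.0% or 0.5% to 2.2%. Those end values are what the stated limits already imply when all patients are observed.

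### The safety trigger never adds related deaths to the non-fatal event count, so some mixed patterns that include deaths continue while an all-non-fatal pattern with no more events stops

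*Combined protocol and SAP*

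**What the plan says.** The Safety Trigger part of the synopsis pools both arms, looks when 12 and 24 subjects are enrolled, and counts events in the first cycle only.

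- At 12, the study stops on "3 incidents of STE excluding mortality, or 2 incidents of mortality deemed not likely to be due to progression of the cancer" and possibly related to treatment.
- At 24, it stops on "5 incidents of STE excluding mortality, or 3 incidents of mortality" with the same qualifier: "deemed not likely to be due to progression of the cancer but possibly related to the treatment".

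Three things are STEs:

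- "Any non-hematologic toxicity grade 3-4 that require delay of treatment by more than 7 days despite optimal management"
- "Any hematologic toxicity grade 3-4 that require delay of treatment by more than 7 days despite optimal management including blood products and growth factors"
- "Any mortality", with no condition on cause.

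The section also promises ongoing safety monitoring, without a threshold or an action attached. It gives no target toxicity rate and no stopping probabilities.

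**The concern.** The definition makes every death an STE, and the trigger then removes every death from the STE count. Related deaths re-enter only through a separate limit, and no limit applies to the two counts together. A subject who dies of treatment without first having a grade 3-4 toxicity that delayed dosing by more than 7 days moves the study no closer to the STE limit. A subject with a survivable toxicity and such a delay does. Mixed patterns can therefore fall between the two limits.

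The text also does not say what happens to a qualifying toxicity that later proves fatal. It may stay in the non-fatal count, or it may be reclassified as a death and leave it.

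At stake is whether the pre-specified stop works when toxicity is partly fatal, in a trial that combines a drug with a diet. A pattern missed at 12 is not formally looked at again until 24, and 42 − 24 = 18 planned patients come after the second look.

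**Working it through.** The plan states no operating characteristic for the trigger, so there is no figure to reproduce.

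**Step 1: enumeration, no assumptions.** Write (a, d) for the number of non-fatal STEs and the number of qualifying deaths.

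- Rule as written: stop at 12 if a ≥ 3 or d ≥ 2; stop at 24 if a ≥ 5 or d ≥ 3.
- Comparison rule, same four limits: stop at 12 if a + d ≥ 3 or d ≥ 2; stop at 24 if a + d ≥ 5 or d ≥ 3.

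The two rules differ in exactly these cells:

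| Look | Stops as written | Continues as written although a + d reaches the STE limit |
|---|---|---|
| 12 | (3,0) | (2,1) |
| 24 | (5,0) | (4,1), (3,2), (4,2) |

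The cells (2,1), (4,1) and (3,2) have the same number of events as the stopping pattern, with one or two of them fatal. The cell (4,2) has six events against five.

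**Step 2: size under assumed rates.** Assumptions: each patient has one outcome (non-fatal STE with probability p, related death with probability q, or neither), patients are independent, and each look is taken separately. Then

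P(a, d) = n! / [a! d! (n−a−d)!] × p^a × q^d × (1−p−q)^(n−a−d),

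and the gain from the comparison rule is the sum over the cells in step 1.

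Worked case, p = 0.15 and q = 0.05:

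- n = 12: P(2,1) = 660 × 0.15² × 0.05 × 0.80⁹ = 0.0997. The chance of stopping goes from 36.0% to 45.9%.
- n = 24: P(4,1) = 212,520 × 0.15⁴ × 0.05 × 0.80¹⁹ = 0.0775; P(3,2) = 425,040 × 0.15³ × 0.05² × 0.80¹⁹ = 0.0517; P(4,2) = 2,018,940 × 0.15⁴ × 0.05² × 0.80¹⁸ = 0.0460. The sum is 0.1752, and the chance goes from 37.7% to 55.2%.

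Other assumed rates, with gains taken before rounding:

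| Non-fatal / fatal | n = 12: written → combined (gain) | n = 24: written → combined (gain) |
|---|---|---|
| 10% / 1% | 11.7% → 14.0% (2.3) | 8.7% → 11.7% (3.0) |
| 10% / 2% | 13.2% → 17.4% (4.2) | 9.6% → 15.7% (6.1) |
| 20% / 1% | 44.6% → 47.7% (3.2) | 54.1% → 58.8% (4.7) |
| 15% / 5% | 36.0% → 45.9% (10.0) | 37.7% → 55.2% (17.5) |
| 20% / 5% | 52.0% → 61.9% (9.9) | 60.4% → 75.8% (15.3) |

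**Step 3: does the rule as written stop less often when events are more often fatal?** Hold p + q at 20% and vary the fatal part q:

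| q | 0% | 1% | 2% | 5% | 10% | 15% | 20% |
|---|---|---|---|---|---|---|---|
| n = 12 | 44.2% | 41.0% | 38.7% | 36.0% | 42.4% | 56.8% | 72.5% |
| n = 24 | 54.0% | 49.1% | 44.7% | 37.7% | 49.2% | 72.3% | 88.5% |

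The chance of stopping falls and then rises. It is below the all-non-fatal value for small fatal shares and above it once deaths dominate.

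**The case against.** Separate limits for fatal and non-fatal events are a legitimate structure. The death limits here are the stricter ones (2 against 3, and 3 against 5), and one more event of either kind never undoes a stop. That stands, but it protects against deaths taken alone. It does not reach the mixed patterns.

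A reader might infer that whenever one of three qualifying toxicities turns fatal, the study drops back below the limit. The documents do not support that. The trigger counts incidents, and nothing deletes a toxicity that has already delayed dosing by more than 7 days because the patient later dies. On that reading the tally is three non-fatal incidents plus a death, and the study stops. The gap is certain only for a related death with no earlier qualifying delay. For the other case the text is silent.

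A reader might also infer that the rule is in general less likely to stop when events are fatal. Step 3 shows that this holds only for small fatal shares.

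Finally, this need not be the trial's only study-level safeguard. The public text is a synopsis that points to Sections 5.6 and 6.6, which it does not reproduce, and it mentions ongoing monitoring. That monitoring has no threshold in the text available, so it does not close the gap.

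**Conclusion.** The concern holds in a limited form. From the wording alone, one pattern at 12 and three at 24 continue although their total, deaths included, reaches the STE limit, and the handling of a toxicity that becomes fatal is undefined.

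The practical size rests on assumed first-cycle rates, one outcome per patient and each look taken separately. In the five rate pairs of step 2, the missed probability is 2 to 10 points at 12 and 3 to 18 points at 24. It is at the low end of those ranges when related deaths are near 1% and at the high end near 5%. The documents give no acceptable toxicity rate, so neither version of the rule can be called correctly calibrated.

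This should be corrected because it concerns participant protection and is cheap to correct. It ranks below must-fix, because deaths have their own stricter limits and the gap is small at low death rates.

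**What to change.** Reconcile the STE definition with the trigger:

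1. Keep the four limits and count treatment-related deaths in both tallies: trigger if STEs including treatment-related deaths reach 3 in the first 12 or 5 in the first 24, or if such deaths alone reach 2 or 3.
2. State that a patient whose qualifying toxicity becomes fatal stays in the STE count, and whether that patient counts once or twice (the calculations above count once).
3. Report the stopping probabilities at each look over a range of non-fatal and fatal rates.

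The cost is a few sentences and one table, with no extra data or patients and no change to any limit. The downside is a higher chance of stopping when a related death occurs alongside other STEs. It is small at about 1% related deaths (2 to 5 points) but not at about 5% (10 to 18 points), so the sponsor should see the table before adopting the wording.
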